Duration of Subject Participation:	Duration of treatment with The MetaNeb® System will be a minimum of 48 hours, or until the subject is discharged from the hospital (if discharge is earlier). Enrolled subjects will remain in the study through Day 4 or until the subject is discharged from the hospital, whichever occurs sooner.
Number of Subjects:	Up to approximately fifteen (15) subjects will be enrolled.
Study Population:	Post-surgical (thoracic, cardiac or abdominal surgery) non-mechanically ventilated patients with significant atelectasis, as documented by chest x-ray results.
Inclusion Criteria	
Patients who meet all of the following inclusion criteria and no exclusion criteria will be included in the study:
 
 • Post-surgical (thoracic, cardiac or abdominal surgery) • Age \geq 18 years • Significant atelectasis by chest x-ray • Patient meets indication for therapy intervention as defined by Recruitment and Airway Clearance Protocol (Respiratory Department Policy and Procedure) • Signed informed consent

Hill-Rom®	Evaluation of The MetaNeb® System to reduce atelectasis as assessed by chest x-ray	Page 8 of 29		
	CBI	06 March 2017	Rev C	CR-RR2016- 001

Exclusion Criteria:	
Patients who meet one or more of the following exclusion criteria will not be eligible for the study:
 
 • Cause of atelectasis suspected to be infectious or solid mass • Requirement for mechanical ventilation • Requirement for chronic supplemental oxygen • Hemodynamically unstable, as defined by need for vasopressor therapy • Anticipated need for mechanical ventilation or other poor clinical outcome, unrelated to atelectasis or secretion retention • Contraindication to MetaNeb® therapy (untreated tension pneumothorax) • Inability to perform MetaNeb® therapy using a mouthpiece • Anticipated hospital discharge within 24 hours

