SpO₂/FiO₂ Ratio: The SpO₂/FiO₂ ratio (based on pulse oximetry readings and the O₂ requirement) for each subject will be calculated for the time of each chest x-ray. The SpO₂/FiO₂ ratio will also be calculated for the beginning of each shift for Day 0 – Day 2, or until the time of discharge from the hospital (if earlier).

Assessment of Dyspnea (Modified Borg Dyspnea Scale): An evaluation of each subject's dyspnea level will be assessed using patient response and a Modified Borg Dyspnea Scale. Evaluation will be completed by respiratory staff at the time of enrollment into the study (Day 0), and on a daily basis for Day 1 and Day 2, or at the time of discharge from the hospital (if earlier).

Respiratory Status Evaluation: An evaluation of each subject's respiratory status will be completed by the physician investigator at the time of enrollment into the study (Day 0) and on Day 2, or at the time of discharge from the hospital (if earlier).

MetaNeb® Treatments: All MetaNeb® treatments will be documented for each day beginning with enrollment (Day 0), Day 1 and Day 2, and through Day 4 or until the time of discharge from the hospital (if earlier).

Hill-Rom®	Evaluation of The MetaNeb® System to reduce atelectasis as assessed by chest x-ray		Page 18 of 29
	CBI	06 March 2017	Rev C

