3.5 Statistical Methods and Analysis

3.5.1 Sample Size Estimation:

The sample size for this study is a convenience sample. The study is designed to provide preliminary information on the benefits of the addition of the MetaNeb® System in treating pulmonary atelectasis and associated hypoxemia. Resulting data on the outcomes associated with The MetaNeb® System may help to provide definition of the effect size and variability and the number of subjects required for subsequent studies.

Subjects with a Kelly Score of one (1) or less in both lungs on the baseline (Day 0) chest x-ray will be excluded from the primary endpoint analysis and secondary endpoint analyses related to Kelly Score.

3.5.2 Statistical Analysis:

- Summary statistics and data listings will be provided.
- Demographic data will be summarized. For continuous type data (e. g. Age), descriptive summary statistics (N, mean, median, standard deviation, min, and max) will be presented. For categorical variables (gender, race, etc.) the number and percent of patients in each category will be provided.

Primary Endpoint:

The Kelly atelectasis score at Day 2 will be summarized with shift tables from baseline. Proportion of subjects showing an improvement from baseline will be summarized.

Secondary Endpoints:

- The Kelly atelectasis score at Day 1 and Day 4/discharge will be summarized with shift tables from baseline.
- Time to a Kelly score of 1 in both lungs will be summarized with a Kaplan-Meier curve, with estimate of the median time and a 95% confidence interval.
- To address possible decrease in sample size over time, due to subjects' improvement and stoppage of use of The MetaNeb® System, the Kelly atelectasis score shift from baseline will also be tabulated using LOCF (last observation carried forward).
- Patient reported level of dyspnea (modified Borg dyspnea scale) will be tabulated for each time point.
- The oxygenation index will be summarized by calculating the mean and standard deviation at each time point, as well as for changes from baseline.

Hill-Rom®	Evaluation of The MetaNeb® System to reduce atelectasis as assessed by chest x-ray		
	CBI	06 March 2017	Rev C

- Chest x-ray improvement using a comparative scale after a minimum of forty-eight (48) hours of therapy with The MetaNeb® System
- Oxygenation index (SpO₂/FiO₂ ratio) at Day 1 and Day 4/discharge compared to baseline
- Change in patient respiratory status (Borg Dyspnea Scale – Appendix 2)

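### Section 3.5.2 treats improving and stopping the device as sample loss to be filled by LOCF, although follow-up and the Kelly film run to Day 4/discharge regardless of device use

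*Combined protocol and SAP*

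**What the plan says.** Three parts of the protocol bear on this.

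- **Follow-up.** The synopsis (Duration of Subject Participation) says: "Enrolled subjects will remain in the study through Day 4 or until the subject is discharged from the hospital, whichever occurs sooner". Table 1 and Sections 3.3 and 3.4.1 place a Kelly-scored film at Day 4/discharge, with no condition on whether the device is still in use. The comparative ranking in Section 3.3 also needs that film, because it ranks four films per subject.
- **Treatment.** The synopsis says that device treatment "will be a minimum of 48 hours, or until the subject is discharged from the hospital" if that comes first. A subject may therefore be off the device but still in the study between Day 2 and Day 4. Section 3.4.1 records this: "All MetaNeb® treatments will be documented for each day beginning with enrollment (Day 0), Day 1 and Day 2, and through Day 4".
- **Analysis.** Section 3.5.2 plans a shift table from baseline for Day 4/discharge. A further bullet anticipates that numbers may fall over time. It names the cause and the remedy together: "improvement and stoppage of use of The MetaNeb® System, the Kelly atelectasis score shift from baseline will also be tabulated using LOCF".

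Section 3.5.2 does not say whether a film taken after the device has stopped enters the ordinary Day 4/discharge table, or whether LOCF may replace such a film. Section 3.1.2 adds that films are collected as they become available, so a scheduled film can be absent.

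**The concern.** The reason that Section 3.5.2 gives for a shrinking sample is not a reason for missing data under the protocol's own schedule. A subject who stops the device and stays in hospital is still in the study and still due a film. A subject discharged early is already covered by the Day 4/discharge definition.

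The stated reason is also the outcome itself. When subjects are missing because they improved, LOCF fixes each of them at the improved score. That is the most favourable value for anyone whose atelectasis could return. The observed-case table drops the same subjects, which distorts it in a direction that depends on how many relapsed. With the 48-hour minimum, this bears mainly on Day 4.

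The synopsis puts a 95% confidence interval on the proportion improved at Day 4/discharge, and Section 3.5.1 says that the data may help to define effect size and sample size for later studies. A Day 4 proportion that depends on an unstated rule is a weak basis for that.

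**Working it through.** **No planned figure to reproduce.** The synopsis says "Up to approximately fifteen (15) subjects will be enrolled", and Section 3.5.1 says "The sample size for this study is a convenience sample". No dropout rate, stopping rate or relapse rate is given. The counts below, other than 15, are assumptions.

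**Step 1. Is a subject who stops the device missing at Day 4?**

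| Situation after Day 2 | Synopsis and Table 1 | Section 3.5.2 |
|---|---|---|
| On device, in hospital | In study, film due | Observed |
| Stopped after improving, in hospital | In study, film due | Given as a cause of sample loss, answered by LOCF |
| Discharged before Day 4 | Discharge film due | Covered by Day 4/discharge |

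The middle row is the conflict.

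**Step 2. Effect on each table.** Let n be the number analysed, a the number improved at Day 2, s the number of those who stop and have no Day 4 film used, and r the number of the s who are no longer better than baseline at Day 4. All others are taken as unchanged.

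- LOCF proportion = a/n, whatever r is
- Observed-case proportion = (a − s)/(n − s)
- Actual proportion = (a − r)/n
- LOCF overstatement = r/n

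**Step 3. Numbers.** Take n = 15, a = 10, s = 5 (a and s assumed). The intervals are exact (Clopper-Pearson) 95% intervals.

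| Quantity | Result |
|---|---|
| LOCF | 10/15 = 66.7% (38.4 to 88.2) |
| Observed cases | 5/10 = 50.0% (18.7 to 81.3) |
| Actual, r = 0 | 10/15 = 66.7% |
| Actual, r = 2 | 8/15 = 53.3% (26.6 to 78.7) |
| Actual, r = 5 | 5/15 = 33.3% (11.8 to 61.6) |

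LOCF equals the actual figure only if no one relapses. The observed-case figure is 66.7 − 50.0 = 16.7 points too low with no relapse and 50.0 − 33.3 = 16.7 points too high if all five relapse.

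**Step 4. Range.** Each hidden relapse adds 1/15 = 6.7 points. With relapse probability p, the expected overstatement is s × p/15, and the chance that at least one relapse is hidden is 1 − (1 − p)^s.

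| p | s = 3 | s = 5 | s = 8 |
|---|---|---|---|
| 10% | 2.0 points (27%) | 3.3 (41%) | 5.3 (57%) |
| 20% | 4.0 (49%) | 6.7 (67%) | 10.7 (83%) |
| 40% | 8.0 (78%) | 13.3 (92%) | 21.3 (98%) |

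Each cell gives the expected overstatement, with the chance of at least one hidden relapse in brackets.

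Section 3.5.1 excludes subjects with a baseline Kelly score of 1 or less in both lungs from the Kelly analyses, so n may be below 15. With 12 analysed, for example, each hidden relapse would add 1/12 = 8.3 points.

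**The case against.** The strongest reply is that nothing in the protocol stops films when the device stops. The Day 4/discharge film is scheduled for everyone, and LOCF ordinarily fills only values that are missing. If the film is taken and used, LOCF hides nothing. LOCF is also an additional tabulation beside the ordinary shift table. Data listings are promised, and the blinded ranking could show a Day 4 film worse than Day 2. The primary endpoint is at Day 2, and the study is small and descriptive.

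Most of this stands, and it rules out three stronger readings that a reader might infer.

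- **That the Day 4 results are biased under a stated rule.** No text drops films taken off the device or tells the site to stop taking them. The distortion arises only where such a film is absent or set aside. Section 3.1.2 makes absence possible, because films are collected as available.
- **That the plan fails to measure how long clearance lasts after treatment.** Sections 2.0 and 3.3 ask about improvement after therapy starts. Durability off the device is not a stated objective.
- **That the planned tables will differ by some particular amount.** The size depends entirely on counts that the documents do not give. A subject who worsens but remains better than baseline still counts as improved, so not every worsening is a relapse in the sense used above.

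The reply does not remove the conflict. Section 3.5.2 still names stopping as a cause of loss and still answers it with the most favourable value. Listings and rankings cannot help where there is no film.

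**Conclusion.** The conflict is in the text and should be resolved. Section 3.5.2 is at odds with the synopsis and Table 1 on whether stopping the device removes a subject from the Day 4 sample. Its LOCF rule is the best-case bound for improved subjects who stop.

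If 15 are analysed, each hidden relapse adds 6.7 points to the LOCF proportion. Over the assumed range of 3 to 8 such subjects and 10% to 40% relapse, the expected overstatement runs from 2.0 to 21.3 points. This rests on three assumptions: those subjects have no usable Day 4 film, a relapse means no longer better than baseline, and the other subjects do not change. The true number of such subjects may be zero.

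The effect is confined to a supplementary table and its observed-case companion for a descriptive secondary endpoint. It is a cheap improvement worth making, and does not undermine the primary analysis.

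**What to change.** 1. Reconcile Section 3.5.2 with the synopsis and Table 1. State that stopping the device does not end follow-up, and that every available Day 4/discharge film is analysed whether or not the device is in use.
2. Remove stopping the device as a reason for LOCF. Use LOCF only in a table labelled as a sensitivity analysis, for films that are truly missing, and give the reason for each. Do not limit it to discharged or withdrawn subjects, since that would leave out inpatients for whom no film became available.
3. Beside it, show a bound that counts improved subjects who stopped and have no film as not improved. In the example above, the pair would be 10/15 = 66.7% and 5/15 = 33.3%.
4. From the treatment log, list device status and time since last treatment at the Day 4/discharge film, and any lung whose score worsened after stopping. Present this as description only. Stopping depends on response, so a comparison of subjects on and off the device would mislead.

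The cost is a few sentences, one extra bound and one listing, all from scheduled films and the existing treatment log. No assessment is added to the schedule, and nothing changes about when therapy stops. The downsides are small cells and a Day 4 figure that may be less favourable than under LOCF.

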4.0 General Study Information

4.1 Technical Support for Product

Technical product support will be performed by Hill-Rom following routine service practices (contact details will be provided).

4.2 Record Retention

Records must be maintained for a period of up to three years after the latter of the following dates: the date the study is completed/terminated, or the date of the last regulatory approval. The Investigators or Institutions shall notify the Sponsor at least thirty (30) days prior to any planned destruction of records from this study.

All records will be kept confidential and the patient's name will not be released at any time. Code numbers will be used to de-identify patient information on the CRFs and other study-related documents.

5.0 Study Procedures

5.1 Informed Consent:

Informed consent must be obtained from all subjects prior to participation as per Federal Regulations and/or the qualifying Institutional Review Board (IRB). A blank copy of the IRB-approved form must be kept on-site and by the sponsor. The signed original for each subject must be kept in the study files, and subjects will be given a copy of their signed informed consent.

5.2 Complaints and Adverse Events Reporting

Hill-Rom®	Evaluation of The MetaNeb® System to reduce atelectasis as assessed by chest x-ray	Page 20 of 29
CBI	06 March 2017	Rev C

During the study, any adverse device effect, device-related complaint or allegation of injury (of any type) must be reported to the Sponsor within 24 hours. Please contact [name] by [contact] (office) PI [REDACTED] or email: [contact].

A complaint is defined as any written, electronic or verbal communication that alleges deficiencies related to the identity, design, quality, durability, reliability, safety, effectiveness or performance of the device. A serious injury is defined as an injury or illness that is life-threatening; results in permanent impairment of a body function or permanent damage to a body structure; or necessitates medical or surgical intervention to preclude permanent impairment of a body function or permanent damage to a body structure.

Any device complaint and/or allegation of injury shall be reviewed, evaluated, and investigated by Hill-Rom Post Market Surveillance and reported to the appropriate Health Authority per current regulations. The Investigators are responsible for informing the Institutional Review Boards, as per their guidelines.

5.3 Deviations from the Study Protocol

A change (other than administrative) to any part of the study protocol must be mutually agreed upon by the Sponsor and the Investigator(s). The Investigator(s) will then submit an amendment to his/her/their institution's local IRB. Until the new protocol is approved, new patients will be included and followed under the current protocol.

5.4 Materials Provided by the Sponsor

The Sponsor will supply The MetaNeb® System devices to the institution.

6.0 Investigator and Sponsor Responsibilities

6.1 Investigator's Responsibilities

The Investigator will comply with Good Clinical Practices (GCPs) and applicable regulatory requirements, as itemized below.

- The Investigator should be familiar with the appropriate use of The MetaNeb® System Device and any other information provided by the Sponsor.
- The Investigator should provide adequate staff to conduct and complete the study within the agreed study time period. The Investigator should ensure that all persons assisting with the study are adequately informed about the protocol, The MetaNeb® System Device and their study related duties.

Hill-Rom®	Evaluation of The MetaNeb® System to reduce atelectasis as assessed by chest x-ray		
	CBI	06 March 2017	Rev C

- A qualified physician delegated as an investigator or sub-investigator will be responsible for all study related duties and functions. During a patients' participation, the Investigator/Institution should ensure that adequate medical care is provided to the patient for any adverse event.
- The Investigator should have written and dated approval from the IRB for the protocol, IC forms or waiver of informed consent, HIPAA authorization, patient recruitment procedures and any other written information for the conduct of the study and/or to be provided to patients.
- The Investigator/Institution should conduct the study in compliance with the protocol agreed to by the Sponsor. The Investigator should sign the protocol or alternative contract to confirm agreement. The Investigator should not implement any deviation or changes to the protocol without agreement with the Sponsor and prior review and agreement from the IRB, unless the deviation or change is to eliminate an immediate hazard to study patients.
- The Investigator/Institution is responsible for all MetaNeb® System Devices that are placed with the Investigator/Institution. When it is allowed, the Investigator may assign Device accountability to another appropriate individual. The Investigator or responsible individual shall maintain records of the Device delivery to the site, inventory at the site and the return to the Sponsor of unused Device or equipment. The MetaNeb® System Device should be stored as specified by the Sponsor and applicable regulatory requirements. The Investigator should ensure that the individual Device is demonstrated and/or used in accordance with the approved protocol. If appropriate and applicable, the Investigator or designee should explain the correct use of The MetaNeb® System Device to each patient.
- In obtaining and documenting informed consent (unless waived), the Investigator should comply with the applicable regulatory requirements and should adhere to GCP and the ethical principles that have their origin in the Declaration of Helsinki.
- The Investigator, per Title 21 Code of Federal Regulations Part 54, should disclose any financial interests that could affect the reliability of the data.
- The Investigator should ensure the accuracy, completeness, legibility and timeliness of the data reported to the Sponsor in the CRFs and required reports.
- The Investigator should maintain the study documents as required by the applicable regulatory requirements. Records must be maintained for a period

Hill-Rom®	Evaluation of The MetaNeb® System to reduce atelectasis as assessed by chest x-ray			Page 22 of 29
	CBI	06 March 2017	Rev C	CR-RR2016- 001

of three years after the latter of the following dates: the date the study is completed/terminated or the date of the last regulatory approval based on the study data. The Investigator or Institution shall notify the Sponsor at least thirty (30) days prior to any planned destruction of records from this study.

- The Investigator should submit written summaries of the status of the study to the IRB annually, or as requested by the IRB, and upon completion of the Study.
- All serious adverse device effects (SADE) and unanticipated adverse device effects (UADE) should be reported immediately to the Sponsor and per the local IRB's reporting policy at that site. The initial reports should be followed by more detailed reports if more information becomes available. If the study is terminated prematurely or suspended for any reason, the Investigator should promptly inform the study patients and ensure appropriate therapy and follow-up is scheduled or documented for each patient.

6.2 Sponsor's Responsibilities

The Sponsor of the program is Hill-Rom Company, Inc. The Sponsor's, responsibilities are itemized below.

- The Sponsor is responsible for implementing and maintaining quality assurance and quality control systems with written standard operating procedures (SOPs) to ensure that studies are conducted and that the data are generated, documented, and reported in compliance with the protocol, GCPs and applicable regulatory requirements. The Sponsor is responsible for securing an agreement from all involved parties to ensure direct access to all study-related sites, source documents, and reports for the purpose of monitoring and auditing.
- The Sponsor may transfer any or all of the study-related duties and functions to a Contract Research Organization (CRO), but the ultimate responsibility for the quality and integrity of the data resides with the Sponsor.
- The Sponsor should use an unambiguous patient identification code that allows for de-identification of all the data reported for each patient.
- The Sponsor should retain the essential documents as required by the applicable regulatory requirements. Records must be maintained for a period of three years after the latter of the following dates: the date the study is completed/terminated or the date of the last regulatory approval.
- The Sponsor should ensure the Investigator(s) selected for the study have the proper qualifications, training, and resources to perform the study adequately.

Hill-Rom®	Evaluation of The MetaNeb® System to reduce atelectasis as assessed by chest x-ray		Page 23 of 29
	CBI	06 March 2017	Rev C CR-RR2016- 001

- The Sponsor shall provide the Investigator(s) with a protocol and an Investigator Brochure (or equivalent documentation) and allow sufficient time for the Investigator to review the information provided.
- The Sponsor should ensure timely delivery of the Device(s) to the Investigator(s); maintain records that document shipment, receipt, disposition, return and destruction (if applicable) of the Devices; maintain a system for retrieving Devices and documenting this retrieval; maintain a system for the disposition of unused Device(s) and for the documentation of this disposition.
- The Sponsor should ensure that it is specified in the protocol or other written agreement that the Investigator(s)/Institution(s) provide direct access to source documents for study-related monitoring, audits, IRB review, and regulatory inspection. The Sponsor should verify that each patient has consented in writing, to direct access to his/her original medical records for study-related monitoring, audit, IRB review and regulatory inspection, or that informed consent has been waived.
- The Sponsor is responsible for submitting reports of all recalls and device disposition to the IRB and the FDA, as applicable.

